12.3. Appendix 3: Assessment Windows

12.3.1. Definitions of Assessment Windows for Analyses

No Assessment Windows will be defined for Analysis, and summaries and analyses will be based on nominal visits.

12.4. Appendix 4: Study Phases and Treatment Emergent Adverse Events

12.4.1. Study Phases

Treatment phases will be defined for Part A and Part B of the study. Therefore, assessments and events will be classified according to the time of occurrence relative to study treatment start date and the Day 43 visit.

Study Phase	Definition
Pre-Treatment	Date ≤ Study Treatment Start Date
On-Treatment	Study Treatment Start Date < Date ≤ Study Treatment Stop Date
On-Treatment (Part A)	Study Treatment Start Date < Date ≤ Day 43 Visit Date
On-Treatment (Part B)	Day 43 Visit Date < Date ≤ Study Treatment Stop Date
Post-Treatment	Date > Study Treatment Stop Date

12.4.1.1. Study Phases for Concomitant Medication

Study Phase	Definition
Prior	If medication end date is not missing and is before 28 days prior to screening visit
Concomitant	Any medication that is not a prior
Post-Treatment	Any medication that is started ≥ Study Treatment Stop Date +1

NOTES:

- Please refer to [Appendix 7: Reporting Standards for Missing Data](#) for handling of missing and partial dates for concomitant medication. Use the rules in this table if concomitant medication date is completely missing.

12.4.2. Treatment Emergent Flag for Adverse Events

Treatment State	Definition
AE = Pre-Treatment	If AE onset date is before treatment start date: = AE Onset Date < Study Treatment Start Date
AE = On-Treatment	If AE onset date is on or after treatment start date and on or before treatment stop date: = Study Treatment Start Date ≤ AE Start Date ≤ Study Treatment Stop Date +1
AE = Post-Treatment	If AE onset date is after the treatment stop date: = AE Start Date > Study Treatment Stop Date +1
AE Onset Time Since 1 st Dose (Days)	If Treatment Start Date > AE Onset Date: = AE Onset Date - Treatment Start Date If Treatment Start Date ≤ AE Onset Date: = AE Onset Date - Treatment Start Date +1 Missing otherwise.
AE Duration (Days)	AE Resolution Date – AE Onset Date + 1
AE = Drug-related	If relationship is marked 'YES' on Inform/CRF OR value is missing.

NOTES:

- If the study treatment stop date is missing, then the AE will be considered to be On-Treatment.

12.5. Appendix 5: Data Display Standards & Handling Conventions

12.5.1. Reporting Process

Software	

 The currently supported versions of SAS software will be used. 	
Reporting Area for Interim Analysis	
HARP Server	UK1SALX00175
HARP Area	arenv \ arprod \ gsk2982772 \ mid202152 \ interim1
QC Spreadsheet	arenv \ arwork \ gsk2982772 \ mid202152 \ interim1 \ documents
Reporting Area for Final Reporting	
HARP Server	UK1SALX00175
HARP Area	arenv \ arprod \ gsk2982772 \ mid202152 \ final
QC Spreadsheet	arenv \ arwork \ gsk2982772 \ mid202152 \ final \ documents
Analysis Datasets	

 Analysis datasets will be created per Integrated Data Standards Library (IDSL) GSK A&R dataset standards. 	
Generation of RTF Files	

 RTF files will be generated for all tables at the time of the SAC. 	

12.5.2. Reporting Standards

General	

 The current GSK Integrated Data Standards Library (IDSL) will be applied for reporting, unless otherwise stated (IDSL Standards Location: https://spope.gsk.com/sites/IDSLLibrary/SitePages/Home.aspx: 
 4.03 to 4.23: General Principles 5.01 to 5.08: Principles Related to Data Listings 6.01 to 6.11: Principles Related to Summary Tables 7.01 to 7.13: Principles Related to Graphics Participant level listings will not be provided in the main body of the GSK Clinical Study Report. All participant level listings will be located in the modular appendices as ICH or non-ICH listings. 	
Formats	

 GSK IDSL Statistical Principles (5.03 & 6.06.3) for decimal places (DP's) will be adopted for reporting of data based on the raw data collected, unless otherwise stated. Numeric data will be reported at the precision collected on the eCRF. The reported precision from non eCRF sources will follow the IDSL statistical principles but may be adjusted to a clinically interpretable number of DP's. 	
Planned and Actual Time	

 Reporting for tables, figures and formal statistical analyses: 
 Planned time relative to dosing will be used in figures, summaries, statistical analyses and calculation of any derived parameters, unless otherwise stated. The impact of any major deviation from the planned assessment times and/or scheduled visit days on the analyses and interpretation of the results will be assessed as appropriate. 	

 Reporting for Data Listings: 
 Planned and actual time relative to study drug dosing will be shown in listings (Refer to IDSL Statistical Principle 5.05.1). Unscheduled or unplanned readings will be presented within the participant's listings. 	
Unscheduled Visits	

 For all safety data: 
 Unscheduled visits will not be included in summary tables. Unscheduled visits will not be included in figures. All unscheduled visits will be included in listings. For efficacy data: 
 Early withdrawal visit will be included in all summary tables, figures and listings Early withdrawal visit will be assigned to closest planned study assessment following withdrawal i.e. for data collected from biopsies at the Day 43 visit or Day 85 visit 	
Descriptive Summary Statistics	
Continuous Data	N, n, mean, median, SD, SE, min, max
Categorical Data	N, n, frequency, %
Graphical Displays	

 Refer to IDSL Statistical Principals 7.01 to 7.13. Placebo in graphs to be shown in Black and GSK2982772 in Green 	

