12.6. Appendix 6: Derived and Transformed Data

12.6.1. General

Multiple Measurements at One Analysis Time Point

 • Mean of the measurements will be calculated and used in any derivation of summary statistics but if listed, all data will be presented. • Participants having both High and Low values for Normal Ranges at any post-baseline visit for safety parameters will be counted in both the High and Low categories of “Any visit post-baseline” row of related summary tables. This will also be applicable to relevant Potential Clinical Importance (PCI) summary tables.
Study Day

 • Calculated as the number of days from First Dose Date: 
 • Ref Date = Missing → Study Day = Missing • Ref Date < First Dose Date → Study Day = Ref Date – First Dose Date • Ref Date ≥ First Dose Date → Study Day = Ref Date – (First Dose Date) + 1

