3.21.	Safety	AE16	Summary of Serious Adverse Events by System Organ Class and Preferred Term (Number of Subjects and Occurrences) (Parts A, B and Follow-up) by Period Treatment	FDAAA, EudraCT	IA SAC [1], SAC [1]
3.22.	Safety	AE1	Summary of Adverse Events Leading to Permanent Discontinuation of Study Treatment or Withdrawal from Study (Part A only) by Randomised Treatment	IDSL	IA SAC [1], SAC [1]
3.23.	Safety	AE1	Summary of Adverse Events Leading to Permanent Discontinuation of Study Treatment or Withdrawal from Study (Parts A, B and Follow-up) by Randomised Treatment	IDSL	IA SAC [1], SAC [1]
3.24.	Safety	AE1	Summary of Adverse Events Leading to Permanent Discontinuation of Study Treatment or Withdrawal from Study (Parts A, B and Follow-up) by Period Treatment	IDSL	IA SAC [1], SAC [1]
Laboratory: Chemistry					
3.25.	Safety	LB1	Summary of Chemistry Changes from Baseline (Parts A, B and Follow-up) by Randomised Treatment	ICH E3	IA SAC [1], SAC [1]
3.26.	Safety	LB1	Summary of Chemistry Changes from Period Baseline (Parts A, B and Follow-up) by Period Treatment	ICH E3	IA SAC [1], SAC [1]
3.27.	Safety	LB1	Summary of Lipids Percentage Changes from Baseline (Parts A, B and Follow-up) by Randomised Treatment	Lipids parameters = LDL Cholesterol, HDL Cholesterol, Total Cholesterol, Triglycerides and Cholesterol/HDL ratio	IA SAC [1], SAC [1]

Safety: Tables					
No.	Population	IDSL / Example Shell	Title	Programming Notes	Deliverable [Priority]
3.28.	Safety	LB1	Summary of Lipids Percentage Changes from Period Baseline (Parts A, B and Follow-up) by Period Treatment	Lipids parameters = LDL Cholesterol, HDL Cholesterol, Total Cholesterol Triglycerides and Cholesterol/HDL ratio	IA SAC[1], SAC [1]
3.29.	Safety	LB17	Summary of Worst Case Chemistry Results by PCI Criteria Post-Baseline Relative to Baseline (Parts A, B and Follow-up) by Randomised Treatment	ICH E3 (i.e. treatment emergent)	IA SAC [1], SAC [1]
3.30.	Safety	LB17	Summary of Worst Case Chemistry Results by PCI Criteria Post-Baseline Relative to Period Baseline (Parts A, B and Follow-up) by Period Treatment	ICH E3 (i.e. treatment emergent)	IA SAC [1], SAC [1]
3.31.	Safety	LB17	Summary of Worst Case Lipids Results by NR Criteria Post-Baseline Relative to Baseline (Parts A, B and Follow-up) by Randomised Treatment	Lipids parameters = LDL Cholesterol, HDL Cholesterol, Total Cholesterol Triglycerides and Cholesterol/HDL ratio	IA SAC [1], SAC [1]

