3.32.	Safety	LB17	Summary of Worst Case Lipids Results by NR Criteria Post-Baseline Relative to Period Baseline (Parts A, B and Follow-up) by Period Treatment	Lipids parameters = LDL Cholesterol, HDL Cholesterol, Total Cholesterol, Triglycerides and Cholesterol/HDL ratio	IA SAC [1], SAC [1]
Laboratory: Hematology					
3.33.	Safety	LB1	Summary of Hematology Changes from Baseline (Parts A, B and Follow-up) by Randomised Treatment	ICH E3	IA SAC [1], SAC [1]
3.34.	Safety	LB1	Summary of Hematology Changes from Period Baseline (Parts A, B and Follow-up) by Period Treatment	ICH E3	IA SAC [1], SAC [1]

Safety: Tables					
No.	Population	IDSL / Example Shell	Title	Programming Notes	Deliverable [Priority]
3.35.	Safety	LB17	Summary of Worst Case Hematology Results by PCI Criteria Post-Baseline Relative to Baseline (Parts A, B and Follow-up) by Randomised Treatment	ICH E3	IA SAC [1], SAC [1]
3.36.	Safety	LB17	Summary of Worst Case Hematology Results by PCI Criteria Post-Baseline Relative to Period Baseline (Parts A, B and Follow-up) by Period Treatment	ICH E3	IA SAC [1], SAC [1]
Laboratory: Urinalysis					
3.37.	Safety	LB1	Summary of Urine Concentration Changes from Baseline (Parts A, B and Follow-up) by Randomised Treatment	ICH E3	IA SAC [1], SAC [1]
3.38.	Safety	LB1	Summary of Urine Concentration Changes from Period Baseline (Parts A, B and Follow-up) by Period Treatment	ICH E3	IA SAC [1], SAC [1]
3.39.	Safety	UR1	Summary of Worst Case Urinalysis Results (Discrete or Character Values) Post-Baseline Relative to Baseline (Parts A, B and Follow-up) by Randomised Treatment	ICH E3	IA SAC [1], SAC [1]
3.40.	Safety	UR1	Summary of Worst Case Urinalysis Results (Discrete or Character Values) Post-Baseline Relative to Period Baseline (Parts A, B and Follow-up) by Period Treatment	ICH E3	IA SAC [1], SAC [1]
Laboratory: Hepatobiliary (Liver)					
3.41.	Safety	LIVER1	Summary of Liver Monitoring/Stopping Event Reporting (Parts A, B and Follow-up) by Randomised Treatment	IDSL	IA SAC [1], SAC [1]
3.42.	Safety	LIVER1	Summary of Liver Monitoring/Stopping Event Reporting (Parts A, B and Follow-up) by Period Treatment	IDSL	IA SAC [1], SAC [1]
3.43.	Safety	LIVER10	Summary of Hepatobiliary Laboratory Abnormalities (Parts A, B and Follow-up) by Randomised Treatment	IDSL	IASAC [1], SAC [1]

Safety: Tables					
No.	Population	IDSL / Example Shell	Title	Programming Notes	Deliverable [Priority]

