3.44.	Safety	LIVER10	Summary of Hepatobiliary Laboratory Abnormalities (Parts A, B and Follow-up) by Period Treatment	IDSL	IA SAC [1], SAC [1]
ECGs					
3.45.	Safety	EG1	Summary of ECG Findings (Parts A, B and Follow-up) by Randomised Treatment	IDSL	IA SAC [1], SAC [1]
3.46.	Safety	EG1	Summary of ECG Findings (Parts A, B and Follow-up) by Period Treatment	IDSL	IA SAC [1], SAC [1]
3.47.	Safety	EG10	Summary of Maximum QTc Values Post-Baseline Relative to Baseline by Category (Parts A, B and Follow-up) by Randomised Treatment	IDSL	IA SAC [1], SAC [1]
3.48.	Safety	EG10	Summary of Maximum QTc Values Post-Baseline Relative to Screening by Category (Parts A, B and Follow-up) by Randomised Treatment	Change relative to average of screening triplicates	SAC[1]
3.49.	Safety	EG10	Summary of Maximum QTc Values Post-Baseline Relative to Period Baseline by Category (Parts A, B and Follow-up) by Period Treatment	IDSL	IA SAC [1], SAC [1]
3.50.	Safety	EG2	Summary of Change from Baseline in ECG Values (Parts A, B and Follow-up) by Randomised Treatment	IDSL	IA SAC [1], SAC [1]
3.51.	Safety	EG2	Summary of Change from Screening in ECG Values (Parts A, B and Follow-up) by Randomised Treatment	Change relative to average of screening triplicates	SAC [1]
3.52.	Safety	EG2	Summary of Change from Period Baseline in ECG Values (Parts A, B and Follow-up) by Period Treatment	IDSL	IA SAC [1], SAC [1]
3.53.	Safety	EG11	Summary of Maximum Increase in QTc Values Post-Baseline Relative to Baseline by Category (Parts A, B and Follow-up) by Randomised Treatment	IDSL	IA SAC [1], SAC [1]

Safety: Tables					
No.	Population	IDSL / Example Shell	Title	Programming Notes	Deliverable [Priority]
3.54.	Safety	EG11	Summary of Maximum Increase in QTc Values Post-Baseline Relative to Screening by Category (Parts A, B and Follow-up) by Randomised Treatment	Change relative to average of screening triplicates	SAC [1]
3.55.	Safety	EG11	Summary of Maximum Increase in QTc Values Post-Baseline Relative to Period Baseline by Category (Parts A, B and Follow-up) by Period Treatment	IDSL	IA SAC [1], SAC [1]
Vital Signs					
3.56.	Safety	VS1	Summary of Change from Baseline in Vital Signs (Parts A, B and Follow-up) by Randomised Treatment	ICH E3	IA SAC [1], SAC [1]
3.57.	Safety	VS1	Summary of Change from Period Baseline in Vital Signs (Parts A, B and Follow-up) by Period Treatment	ICH E3	IA SAC [1], SAC [1]

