12.10.6. Safety Figures

Safety: Figures					
No.	Population	IDSL / Example Shell	Title	Programming Notes	Deliverable [Priority]
Adverse Events					
3.1.	Safety	AE10	Plot of Common ($\geq 10\%$) Adverse Events and Relative Risk (Part A only) by Randomised Treatment	IDSL	IA SAC [1], SAC [1]
3.2.	Safety	AE10	Plot of Common ($\geq 10\%$) Adverse Events and Relative Risk (Parts A, B and Follow-up) by Randomised Treatment	IDSL	IA SAC [1], SAC [1]
3.3.	Safety	AE10	Plot of Common ($\geq 10\%$) Adverse Events and Relative Risk (Parts A, B and Follow-up) by Period Treatment	IDSL	IA SAC [1], SAC [1]
Laboratory					
3.4.	Safety	LIVER14	Scatter Plot of Maximum Versus Baseline for ALT (Parts A, B and Follow-up) by Randomised Treatment	IDSL	IA SAC [1], SAC [1]
3.5.	Safety	LIVER14	Scatter Plot of Maximum Versus Period Baseline for ALT (Parts A, B and Follow-up) by Period Treatment	IDSL	IA SAC [1], SAC [1]
3.6.	Safety	LIVER9	Scatter Plot of Maximum ALT Versus Maximum Total Bilirubin ALT (Parts A, B and Follow-up) by Randomised Treatment	IDSL	IA SAC [1], SAC [1]
3.7.	Safety	LIVER9	Scatter Plot of Maximum ALT Versus Maximum Total Bilirubin (Parts A, B and Follow-up) by Period Treatment	IDSL	IA SAC [1], SAC [1]

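### The ban on unscheduled visits in safety tables and figures also covers the worst-case, maximum and hepatobiliary displays, which then show only scheduled values

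*SAP*

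**What the plan says.** Section 12.5.2, under unscheduled visits, sets one rule for all safety data: "Unscheduled visits will not be included in summary tables" and "Unscheduled visits will not be included in figures". Listings are to contain every unscheduled visit. The same section, under its general points, adds: "Participant level listings will not be provided in the main body of the GSK Clinical Study Report".

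Sections 12.10.5 and 12.10.6 then plan displays defined by an extreme or an any-time abnormality. Examples are:

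- Table 3.29: "Summary of Worst Case Chemistry Results by PCI Criteria Post-Baseline Relative to Baseline (Parts A, B and Follow-up) by Randomised Treatment"
- Table 3.43: "Summary of Hepatobiliary Laboratory Abnormalities (Parts A, B and Follow-up) by Randomised Treatment"
- Table 3.53: "Summary of Maximum Increase in QTc Values Post-Baseline Relative to Baseline by Category (Parts A, B and Follow-up) by Randomised Treatment"
- Figure 3.7: "Scatter Plot of Maximum ALT Versus Maximum Total Bilirubin (Parts A, B and Follow-up) by Period Treatment"

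Section 12.6.1 says that participants with both high and low values "at any post-baseline visit for safety parameters will be counted in both the High and Low categories" of an any-visit row, and extends this to the tables of potential clinical importance (PCI).

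**The concern.** Leaving unscheduled values out of a by-visit table is sensible, because they belong to no nominal visit. A worst-case or maximum table has a different purpose: it reports the most extreme value each participant reached after baseline, whenever it was measured. Unscheduled tests are often repeats or are prompted by a symptom or an abnormal result, so they are where an extreme value may well be found. Under the written rule these displays report the worst scheduled value under a title that promises the worst value.

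Safety and tolerability is the primary objective and no hypothesis is tested for it (Section 2.4). The descriptive displays are therefore the primary result. A participant could be listed with a PCI value yet be counted in the table as having none.

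**Working it through.** The SAP states no figure to reproduce. The check is whether anything in the text lets unscheduled values into these displays, followed by a count of what is affected.

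**1. Search for an exception**

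| Place in the SAP | What it says | Admits unscheduled values? |
|---|---|---|
| 7.2 and 7.3, laboratory and other safety analyses | Types of display and treatment groupings | No |
| 12.3.1, assessment windows | No windows; nominal visits are used | No; an unscheduled value cannot be mapped to a planned visit |
| 12.5.2, general points | The sponsor's display standard applies unless the SAP states otherwise | No; the unscheduled-visit rule does state otherwise |
| 12.6.1, general derivations | Double counting of participants with both high and low values | Not addressed |
| 12.7.1, premature withdrawals | Planned data of withdrawn participants enter tables and figures unless otherwise specified | No |
| 12.8, PCI criteria | Thresholds only | No |
| 12.10.5 and 12.10.6, programming notes of the affected displays | Source standard, lipid parameters, or screening triplicates as reference | No |

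**2. Displays affected**

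| Display | Numbers | Count |
|---|---|---|
| Worst-case chemistry and lipids | Tables 3.29–3.32 | 4 |
| Worst-case haematology | Tables 3.35–3.36 | 2 |
| Worst-case urinalysis | Tables 3.39–3.40 | 2 |
| Hepatobiliary abnormalities | Tables 3.43–3.44 | 2 |
| Maximum QTc | Tables 3.47–3.49 | 3 |
| Maximum QTc increase | Tables 3.53–3.55 | 3 |
| Worst-case vital signs | Tables 3.58–3.59 | 2 |
| Maximum ALT, and maximum ALT against maximum bilirubin | Figures 3.4–3.7 | 4 |

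Tables: 4 + 2 + 2 + 2 + 3 + 3 + 2 = 18 of the 59 listed in Section 12.10.5. (The numbering overview in 12.10.1 stops at 3.56; the list itself runs to 3.59.) Figures: 4 of 7.

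**3. Gaps between scheduled tests**

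In the schedule (12.2.1), on-treatment chemistry, haematology, ECG and vital signs after Day 1 fall on Days 15, 29, 43, 57, 71 and 85, nominally 14 days apart. Urinalysis is not required on Days 29, 57 and 71, which leaves Days 15, 43 and 85, with gaps of 28 and 42 days. The schedule's ECG footnote also provides for triplicate recordings when stopping criteria are met. Such a recording made outside a planned visit would be missing from the maximum-QTc tables.

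**4. Effect of one participant**

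Section 2.3 gives approximately 36 participants randomised 2:1. Taking exactly 36, all treated:

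- Active: 36 × 2/3 = 24, so one participant is 1/24 = 4.2 percentage points.
- Placebo: 36 × 1/3 = 12, so one participant is 1/12 = 8.3 points.
- Active column by period treatment: at most 24 + 12 = 36 if every placebo participant enters Part B, so 1/36 = 2.8 points, and more if fewer do.

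How many participants would have an excursion only at an unscheduled test cannot be derived from the SAP.

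**The case against.** The strongest reply is that this is an explicit, pre-specified data rule, and that a worst case over the admitted visits is still a worst case over those visits. Section 12.6.1 settles double counting and does not say which visits are eligible, so it can be followed with scheduled visits alone. No value is lost: unscheduled results go into the listings, including those dedicated to PCI values (30, 31 and 33 for laboratory, 35–38 for ECG, 41–42 for vital signs). Liver monitoring and stopping events have their own Tables 3.41–3.42, titled as event reporting. Adverse events are classified by onset date (12.4.2), so an abnormality reported as an adverse event is tabulated whatever the visit type. The display specifications (Appendix 11) are not shown and might deal with the matter. The percentage shifts are simply 1/n.

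Much of this stands as mitigation. Section 12.6.1 is a tension to reconcile, not a second rule that proves a contradiction, and the point does not depend on it. The listings and the event tables reduce the harm, and placing listings outside the main report affects only where a reader finds the value. The disagreement between table and listing comes from the exclusion itself. None of this restores the missing values to displays whose titles claim the extreme. Unseen specifications cannot be assumed to override an unqualified rule in the SAP. If the programmers do intend to include unscheduled values, the written rule is wrong and still needs correcting.

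**Conclusion.** The concern holds. As written, 18 safety tables and 4 safety figures exclude unscheduled values, and all but the two hepatobiliary abnormality tables have titles promising a worst-case or maximum value. They can understate the number of participants with a clinically important value and can disagree with the listings.

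The display counts come directly from the SAP. The shifts of 4.2, 8.3 and 2.8 points per participant are illustrative: they assume exactly 36 treated participants at 2:1, whereas enrolment is approximate and withdrawn participants may be replaced (12.7.1). The number of participants affected is unknown and may be zero. The adverse-event tables and the by-visit change-from-baseline summaries are outside this point, and Tables 3.41–3.42 are not counted. This should be fixed before the tables are programmed.

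**What to change.** In Section 12.5.2, restrict the exclusion to by-visit summaries and by-visit plots. Add a sentence stating that all post-baseline values, scheduled and unscheduled, enter Tables 3.29–3.32, 3.35–3.36, 3.39–3.40, 3.43–3.44, 3.47–3.49, 3.53–3.55 and 3.58–3.59 and Figures 3.4–3.7. The any-visit wording in Section 12.6.1 would then agree with it.

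The cost is one sentence in the SAP and a small change to the record selection in the affected programs. No new data are needed, and the by-visit tables do not change.

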Treatment Assignment	
 • At Screening a unique CRF number (Subject Number) is assigned. • Participants who meet screening eligibility criteria and complete pre-treatment assessments are randomised through an Interactive Response Technology System (IRTS). The IRTS confirms the participant's CRF number (Subject Number) and provides the randomisation number. • The randomisation number is generated by Clinical Statistics, prior to the start of the study, using validated internal software. Once assigned, this randomisation number must not be reassigned to any other participant in the study. • The randomisation is centrally controlled by the IRTS. • Approximately 36 participants were randomised in a 2:1 ratio to receive GSK2982772 60mg TID or Placebo TID in Part A. • Any participant that is re-screened outside of the allowed screening window at the approval of the GSK Medical Monitor, must be assigned a new unique Subject Number.

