12. APPENDICES

12.1. Appendix 1: Protocol Deviation Management and Definitions for Per Protocol Population

12.1.1. Exclusions from Per Protocol Population

A participant meeting any of the following criteria will be excluded from the Per Protocol population:

Number	Exclusion Description
01	Inclusion #9 – Informed Consent: Informed Consent not available at site or Patient did not sign or date
02	Inclusion #2 – Eligibility: Other medical conditions
03	Inclusion #3 – Eligibility: Confirmed diagnosis of UC
04	Inclusion #4 – Eligibility: Total Mayo score and endoscopy subscore
05	Inclusion #5 – Eligibility: Stable concurrent medication
06	Inclusion #6 – Eligibility: Prior treatment
07	Incorrect randomisation or study unblinding procedures

A participant meeting any of the following criteria will be reviewed for exclusion from the Per Protocol population:

Number	Exclusion Description
08	Exclusion #17 – Concomitant Medication

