8. Sigmoidoscopy may be performed on a separate day within the Day 43 visit window allowance (± 3 days). A separate visit to perform sigmoidoscopy is only allowed to accommodate scheduling. This separate visit should be done before the full Day 43 visit where PK, clinical laboratory tests and all other required Day 43 procedures are performed. Participants must not take their study medication at home in the morning before the sigmoidoscopy procedure and also the morning before the full Day 43 visit, if being done on a separate day. Dispensing of study medication must be done at the 2nd visit (if separate visits are performed).
9. Biopsy only required at Early Withdrawal visit if after at least 14 days of treatment and prior to Day 43 or if after Day 57 and prior to Day 85.
10. Participants must take study medication three times a day approximately 8 hours apart. Exact time of dosing to be recorded in diary cards. On Day 43 and 85, participants must not take their study medication at home in the morning. Participant will complete specified pre-dose assessments and then will be administered their morning dose of medication at site on Day 43. On Day 85, participants are no longer receiving study medication.
11. In Part A, participants will be randomised 2:1 to GSK2982772 60 mg or placebo three times daily for 42 days. At the Day 43 visit, all participants who have completed Part A, will move in to Part B open label treatment with GSK2982772 60 mg three times daily for 42 days.
12. If urine pregnancy test is positive, a confirmatory serum pregnancy test must be performed.
13. Urinalysis not required on Days 29, 57 and 71.
14. Participants can provide a faecal sample at any time during the screening window and up to 48 hours prior to any visit where FCP is being collected. Please see laboratory manual for full details on sample handling and procedure.
15. Blood samples for exploratory biomarkers and Target engagement. See laboratory manual for full details on sample collection, handling and shipment.
16. PK blood samples for GSK2982772 will be taken pre-dose on Day 43. Post-dose serial PK samples will be taken on Days 1 and Day 43 at the following time points: 1, 2, 4, and 6 hours and trough on Day 85 or Early Withdrawal.

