17. A PGx blood sample is collected at the baseline visit (Day 1), after the participant has been randomized and provided informed consent for genetic research. If the sample is not collected at the baseline visit, it can be collected at any time during the study after randomization.
18. Visit windows during the treatment period are relative to Day 1.
19. If a participant withdraws from the study, every effort will be made for the participant to complete an Early Withdrawal visit prior to the Follow Up visit.
20. Follow-up visit should be completed 28 days (± 3 days) after the last dose of study medication.

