12.7. Appendix 7: Reporting Standards for Missing Data

12.7.1. Premature Withdrawals

Element	Reporting Detail
General	
 Participant study completion was defined as one who has completed all phases of the study including the follow-up visit. Withdrawn participants may be replaced in the study at the discretion of the investigator. All available data from participants who were withdrawn from the study will be listed and all available planned data will be included in summary tables and figures, unless otherwise specified.

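### The SAP has no rule for efficacy values observed after a UC medication the protocol does not allow, so in the Safety population a failure improved by other therapy can be counted as a responder

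*SAP*

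**What the plan says.** **Use of withdrawn participants' data.** Section 12.5.2 gives two lines for efficacy. The first is "Early withdrawal visit will be included in all summary tables, figures and listings". The second is "Early withdrawal visit will be assigned to closest planned study assessment following withdrawal", glossed at once as "i.e. for data collected from biopsies at the Day 43 visit or Day 85 visit". Section 12.7.1 sets the general default: "all available planned data will be included in summary tables and figures, unless otherwise specified".

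**Timing of the early-withdrawal visit.** Footnote 19 to the schedule in 12.2.1 says only that "every effort will be made for the participant to complete an Early Withdrawal visit prior to the Follow Up visit". Footnote 20 puts Follow Up 28 (±3) days after the last dose. Footnote 9 limits when a biopsy is needed: "Biopsy only required at Early Withdrawal visit if after at least 14 days of treatment and prior to Day 43", with a second window after Day 57 and before Day 85.

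**Populations.** Section 8.1.1 analyses Mayo in the Safety, PP and PP + Completers sets, and all other efficacy in the Safety set alone. Under section 4, one dose is enough for the Safety set, while PP + Completers requires completion of Parts A and B and Follow-up. Section 12.1.1 lists "Exclusion #17 – Concomitant Medication" among the items to be reviewed for PP exclusion, not among the automatic exclusions.

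**Definitions.** The Mayo response and remission rules and the UCEIS remission rule that can be read in 12.6.4 depend on scores only.

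**The concern.** A participant may do badly, start another UC therapy and then be assessed. The value obtained exists, so it is not a missing-data problem, but it reflects a different treatment. There are two ways in which it can enter the results:

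- The participant withdraws, is seen at an early-withdrawal visit after other therapy has begun, and the result is assigned to Day 43 or Day 85.
- The participant takes the other therapy, stays in the study and attends Day 43 or Day 85 as scheduled.

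In neither case does the SAP recode or remove the value in the Safety population. This matters most at Day 43. Everyone who completes Part A then moves to open-label drug, so Day 43 is the only placebo-controlled visit for the binary endpoints listed in 8.1.2.1.2. With a small placebo arm, a single such result is visible in the response rate.

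**Working it through.** The SAP states no response rate, dropout rate or frequency of other therapy, so there is no planned figure to reproduce.

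**1. Arm sizes.** Section 2.3: "Approximately 36 participants were randomised in a 2:1 ratio to receive GSK2982772 60mg TID or Placebo TID in Part A". Hence 36 × 2/3 = 24 active and 36 × 1/3 = 12 placebo.

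**2. Weight of one participant.** Placebo: 1/12 = 8.3 points. Active: 1/24 = 4.2 points.

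**3. Illustration.** Assumed, not from the SAP: true Day 43 response of 8/24 active and 2/12 placebo, with 0 to 3 failures in one arm counted as responders after other therapy. Difference = active rate − placebo rate; odds ratio = active odds ÷ placebo odds.

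| Failures counted as responders | Active | Placebo | Difference (points) | Odds ratio |
|---|---|---|---|---|
| None | 8/24 | 2/12 | 16.7 | (8/16)/(2/10) = 2.5 |
| 1 placebo | 8/24 | 3/12 | 8.3 | (8/16)/(3/9) = 1.5 |
| 2 placebo | 8/24 | 4/12 | 0.0 | (8/16)/(4/8) = 1.0 |
| 3 placebo | 8/24 | 5/12 | −8.3 | (8/16)/(5/7) = 0.7 |
| 1 active | 9/24 | 2/12 | 20.8 | (9/15)/(2/10) = 3.0 |
| 2 active | 10/24 | 2/12 | 25.0 | (10/14)/(2/10) = 3.6 |
| 3 active | 11/24 | 2/12 | 29.2 | (11/13)/(2/10) = 4.2 |

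Placebo cases shrink the difference and active cases widen it.

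**4. Expected size over a range.** Let q be the share of failures who take other therapy and s the chance that they then meet the response rule. An arm's rate p becomes p + (1 − p)·q·s. For q from 0.05 to 0.30 and s of 0.3 or 0.5 (assumed), the 16.7-point difference becomes 15.4 to 4.2 points if only placebo failures are affected. If both arms are affected alike, it becomes 16.4 to 14.2 points. For example, with q = 0.30 and s = 0.5, placebo is 0.167 + 0.833 × 0.15 = 0.292 and 0.333 − 0.292 = 0.042. The effect is large only when the two arms differ in their use of other therapy.

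**5. The 30% condition for the GEE.** Section 8.1.2.1.2 runs the model only if some group reaches 30% at Day 85. Since 0.30 × 12 = 3.6 and 0.30 × 24 = 7.2, the condition needs 4/12 or 8/24; 3/12 (25.0%) and 7/24 (29.2%) fall short. One case can decide whether the model is fitted.

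**6. Reach of the existing safeguards.**

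- PP review: discretionary, with no stated criterion, and Mayo only.
- PP + Completers: removes every early withdrawal, and so closes that route, but for Mayo only. A participant who took other therapy and completed the study stays in unless the review removes them.
- UCEIS, CRP, FCP, histology and IBDQ: neither safeguard applies.

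**7. Reach of the mapping.** If the gloss in 12.5.2 limits the mapping to biopsy data, it carries forward only histology among the efficacy endpoints. No binary endpoint then receives an early-withdrawal value by this rule, and the scheduled-visit route is what remains for response and remission. If the mapping covers all efficacy data, both routes apply. The text supports either reading, and section 12.3.1, which bases all analyses on nominal visits, does not settle it.

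**The case against.** The strongest objection is that the SAP never says that values after rescue or prohibited therapy are to be used. It does not mention rescue, and the effect follows from general defaults plus silence. Whether such medication may be started, and whether it leads to withdrawal, belongs to the protocol, which is not shown. That stands as a limit on how likely the situation is. It does not supply the analysis rule: the SAP itself decides how recorded values enter its displays, and its defaults favour inclusion.

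Using observed data whatever other therapy was taken is also a recognised treatment-policy approach, and efficacy here is preliminary, with safety as the primary objective. This stands for the continuous endpoints, where setting values to missing would be a different estimand rather than a correction. It is weaker for response and remission, where a success produced by another drug is credited to the randomised arm.

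A reader might infer more than the documents support in four places:

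- **That the mapping moves every efficacy result forward.** The gloss speaks of biopsies. CRP, FCP and IBDQ are not biopsy data.
- **That the early-withdrawal visit has no practical time limit.** On the natural reading of footnote 9, a required biopsy assigned to Day 43 falls between about Day 15 and Day 42, which leaves little time to stop, start other therapy and heal. An early-withdrawal result taken before other therapy carries a failure forward as a failure.
- **That no endpoint definition has a medication condition.** The Mayo endoscopy remission definition is not visible in the text at hand and other parts are redacted, so this can be said only of the definitions that can be read.
- **That the bias must work against the drug.** More use of other therapy on placebo is plausible if the drug works, but the SAP gives no data on it and active cases act in the opposite direction.

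**Conclusion.** The point holds as a gap in the analysis rules, not as a stated instruction. In the Safety population, observed efficacy values are used whatever UC therapy preceded them, so a failure improved by a medication the protocol does not allow can be counted as a responder for the randomised arm. The SAP's safeguards are partial and confined to Mayo.

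The firm figures are the weights: 8.3 points per placebo case and 4.2 points per active case, resting on 36 participants at 2:1. The differences and odds ratios in the table rest on assumed counts and only show sensitivity. The number of cases and the net direction cannot be derived from the SAP. The gap is worth closing because Day 43 is the only controlled visit for the binary endpoints and the arms are small.

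**What to change.** - **Sections 8.1.2.1.2 and 12.6.4.** Count a participant as a non-responder and non-remitter at any visit after starting, or increasing, a UC medication that the protocol does not allow. Flag these cases from the concomitant-medication data before the arms are compared. Keep the as-observed result as a sensitivity display.
- **Section 12.5.2.** Do not assign an early-withdrawal value collected after such medication to Day 43 or Day 85 as an ordinary result. State whether the mapping covers all efficacy data or biopsy data only, and reconcile it with 12.3.1.
- **Section 8.1.2.1.1.** Leave the main MMRM as planned and add a sensitivity MMRM that sets values after such medication to missing.

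These are analysis rules only; which medications are allowed stays with the protocol. The cost is SAP wording, one derived flag and a few extra displays. Sections 6.1.1 and 12.6.2 already have the clinical and medical team identify glucocorticoids and immunosuppressants for the baseline table, so the review need only be extended to changes after baseline. The downside is that response rates may be slightly less favourable.
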